3.1.1. Category I

- Subjects should have not received any collagenase treatments since the completion of the double-blind study.
- Subjects in which the maximum composite response was ONLY a 1-level composite improvement in cellulite severity at Day 71 as assessed by the PR-PCSS and CR-PCSS in either (or both) buttock(s) in the double-blind study. In cases where improvement was in both buttocks, the composite improvement of 1-level must have occurred in the same buttock (ie, the PR-PCSS and CR-PCSS improvement observed in the same buttock).
- Subjects who showed a 2-level improvement in one scale but only a 1-level improvement in the other scale, provided the composite improvement of 1-level was within the same buttock.
- Only buttocks with a composite 1-level improvement or less will be retreated.

- These subjects will be observed for time to reduction of response (defined in section 4.4.1) and safety approximately every 6 months for 2 years and will be observed annually for up to 3 years (Day 1080) from Day 71 of the double-blind study.

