3.1.2. Category II

Subjects should have not received any collagenase treatments since the completion of double-blind study.

Subjects who showed an improvement in cellulite severity of at least two levels in at least one buttock in both the PR-PCSS and the CR-PCSS (ie, 2-level composite responder) in the double-blind study.

These subjects will be observed for time to reduction of response (defined in section 4.4.1) and safety approximately every 6 months for 2 years and will be observed annually for up to 3 years (Day 1080) from Day 71 of the double-blind study.

- Category II subjects must have at least 1-level composite response reduction (ie, reduction of response by at least 1-level in the PR-PCSS and CR-PCSS ratings) compared to Day 71 of the double-blind study (EN3835-302/303) AND no longer maintain 2-level composite response compared to baseline in the EN3835-302/303 study on either or both buttocks to be eligible for a retreatment course. If there is a composite worsening of cellulite severity, the confirmation of loss of response will be established during a follow-up visit ~2 weeks after the loss of response is detected at Day 180, if the loss of response is not confirmed then the subject will not be eligible for retreatment in this study.

One and only one retreatment course in up to 2 qualifying buttocks concurrently will be offered to eligible Category I and Category II subjects during this 3-year study. The subjects in Category I and/or eligible Category II subjects will receive a retreatment course consisting of 3 treatment sessions separated by 21 days (Day 1, 22, and 43). Each treatment session will consist of 12 injections (0.07 mg/0.3 mL per injection) of CCH for a dose of 0.84 mg and volume of 3.6 mL (identical to the treatment course administered in the double-blind study), in each qualifying buttock (see

Table 5) in up to two buttocks treated concurrently.

After initiation of retreatment, the safety and cellulite severity will be assessed on Days 22, 43, and 71. The Category I and Category II subjects who received retreatment will have safety assessment completed during the observational visits at Months 12, 18, 24, and 36 from Day 71 of the double-blind study.

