Complete Loss of Response	Worsening of cellulite severity improvement on PR-PCSS and CR-PCSS ratings in this study prior to retreatment compared to the score at Day 71/EOS in the double-blind studies, where cellulite severity returns to baseline levels of the double-blind studies (ie, Day 1 of the double-blind studies) or worse.	Worsening of cellulite severity improvement on PR-PCSS and CR-PCSS ratings compared to the score at Day 71/End of Treatment Session in the open-label treatment phase, where cellulite severity returns to baseline levels of the retreatment phase (ie, Day 1 of the open-label retreatment phase) or worse.
Time to Complete Loss of Response	Number of days from the time of assessing composite improvement in cellulite severity on PR-PCSS and CR-PCSS at Day 71/EOS in the double-blind study to the study visit prior to retreatment at which the complete loss of response in both PR-PCSS and CR-PCSS is observed.	Number of days from the time of assessing composite improvement in cellulite severity on PR-PCSS and CR-PCSS at Day 71/End of Treatment Session in the open-label treatment phase to the study visit during observation phase after retreatment at which the complete loss of response in both PR-PCSS and CR-PCSS is observed.
2-level Improvement	Improvement in cellulite severity at least by 2 levels on PR-PCSS or CR-PCSS ratings from Day 1 of double-blind study (ie, change from baseline PR-PCSS and/or CR-PCSS rating of -2, or -3).	Improvement in cellulite severity at least by 2 levels on PR-PCSS or CR-PCSS ratings after receiving the retreatments compared to the corresponding rating at Day 1 of the Treatment Session of this study (ie, change from baseline PR-PCSS and/or CR-PCSS rating of -2, or -3).
1-level Improvement	Improvement in cellulite severity at least by 1 levels on PR-PCSS or CR-PCSS ratings from Day 1 of double-blind study (ie, change from baseline PR-PCSS and/or CR-PCSS rating of -2, or -3).	Improvement in cellulite severity at least by 1 levels on PR-PCSS or CR-PCSS ratings after receiving the retreatments compared to the corresponding rating at Day 1 of the Treatment Session of this study (ie, change from baseline PR-PCSS and/or CR-PCSS rating of -2, or -3).

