5. ANALYSIS POPULATIONS

The study will use following analyses population for data summarization.

Table 16: Analysis Population

Population	Definition	Displays
Day-180 Observational Population	The Day-180 Observational Population includes all rollover subjects from studies EN3835-302/303.	The protocol deviations, demographic characteristics and safety analysis for the data obtained from Screening to Day 180 will be based on this population. The reduction of response, complete loss of response, and all cellulite assessments (ie, changes in CR-/PR-PCSS, PR-CIS, S-GAIS, SSRS, and subject satisfaction with cellulite treatment at Day 180 will be summarized.
Prior to Day 180 Population	Prior to Day 180 Population includes all subjects who did not meet inclusion criteria #2 or inclusion criteria #5 or those who withdrew from the study due to SAE/AE, or lost to follow-up prior to Day 180.	The protocol deviations, demographic characteristics and safety analysis for the data obtained from Screening to Day 180 will be based on this population.
Open Label Observation Population	The Open Label Observation Population includes all subjects who enter the open-label study and received active CCH in EN3835-302 or EN3835-303. This population will include all Category I, II, and III subjects including the subjects who received retreatment in the Open-label Period.	The protocol deviations, demographic characteristics and safety parameters for the open label period prior to retreatment will be summarized based on this population.
Time to Reduction of Response (TRR) Population Before Retreatment	The TRR Population Before Retreatment includes all subjects who have at least a 1-level or 2-level improvement in both CR-PCSS and PR-PCSS ratings during the double-blind study for either/both treated buttocks. This population will include Category I and II subjects. Reduction of response will be evaluated separately for subjects who have at least a 1-level and 2-level improvement in both CR-PCSS and PR-PCSS ratings during the double-blind study in each treated buttock. The reduction of response prior to retreatment will be analyzed using this population.	The analyses of cellulite assessments prior to retreatment, and demographic characteristics will be based on this population.

Table 16: Analysis Population (Continued)

Population	Definition	Displays

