7.6.2. Reduction of response using PR-PCSS and CR-PCSS Prior to Retreatment

The proportion of subjects or buttocks with reduction of response (refer to section 4.4.1) will be summarized using frequency counts and percentages using TRR Population Before Retreatment and OLNLR Population subject category (ie, Category I and II, and Overall) and treatment area (ie, left and/or buttock) at the following visits prior to retreatment: Day 180, Month 12, 18, 24, and 36 where reduction of response is assessed.

The proportions will be computed based upon number of subjects within each category and treatment area remains not-retreated prior to that visit.

The following efficacy end points for reduction of response will be summarized:

- Proportion of subjects with 2-level composite reduction
- Proportion of subjects with 1-level composite reduction
- Proportion of subjects with complete loss of response

The time to composite reduction of response (ie, by 1-level and 2-level separately) and time to complete loss of response (refer to section 4.4.1 for derivation) will be summarized descriptively using TRR Population Before Retreatment and OLNLR Population.

The listings of cellulite PR-PCSS and CR-PCSS severity ratings will be provided for All Subjects prior to retreatment.

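### The durability denominators in SAP 7.6.2 and 7.6.3 do not carry the per-buttock response condition of Table 16, so the left/right tables can include buttocks that had no response at the reference Day 71

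*SAP*

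**What the plan says.** **Subject-level labels.** Category I (3.1.1) covers "Subjects in which the maximum composite response was ONLY a 1-level composite improvement in cellulite severity at Day 71". Category II (3.1.2) needs "an improvement in cellulite severity of at least two levels in at least one buttock". Both labels therefore follow the better side. Entry to the TRR Population Before Retreatment (section 5, Table 16) works the same way; it asks for improvement "during the double-blind study for either/both treated buttocks".

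**Buttock-level intent.** The same Table 16 entry adds: "Reduction of response will be evaluated separately for subjects who have at least a 1-level and 2-level improvement in both CR-PCSS and PR-PCSS ratings". The sentence goes on to attach this to each treated buttock. The entry for the TRR Population After Retreatment has a parallel sentence, and the protocol text reproduced in Table 18 is to the same effect.

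**What is tabulated.** Section 7.6 summarises open-label efficacy by subject category and by left or right buttock. Section 7.6.2 reports "The proportion of subjects or buttocks with reduction of response" and gives the denominator: "The proportions will be computed based upon number of subjects within each category and treatment area remains not-retreated prior to that visit". Section 7.6.3 has the same structure, with subjects retreated before the visit as denominator.

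**Event definitions.** Table 13 (4.4.2) defines composite reduction as worsening on both scales from the Day 71 score. Complete loss before retreatment is worsening "where cellulite severity returns to baseline levels of the double-blind studies", or beyond them.

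**The concern.** Time to reduction of response is the only secondary objective (2.2), and 7.6.2 and 7.6.3 are where it is reported. A durability rate is meaningful only among units that had a response to keep. A subject qualifies on one buttock, yet both of her buttocks can appear in the left and right tables under her category, because the stated denominators depend only on category, side and retreatment status.

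Two kinds of buttock may then be misplaced: one with no composite response at the reference Day 71, and a 1-level buttock of a Category II subject, tabulated among the 2-level responders. The second matters because a buttock that improved exactly one level on both scales is back at Day 1 after worsening one level, while a 2-level buttock must worsen at least two on each.

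The SAP also leaves the unit open between subjects and buttocks. Two programmers could follow it faithfully and produce different durability tables.

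**Working it through.** The SAP states no rate for this point, so there is no figure of its own to reproduce. The check has three parts.

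**1. Can the categories stand in for the Table 16 strata?** No. Table 16 uses at least 1-level and at least 2-level improvement, per buttock. Category I means a best response of one level only, per subject. The groups differ in both threshold and unit.

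**2. How Table 13 scores a buttock without a composite response.** Scores are PR-PCSS/CR-PCSS, each 0 to 4, judged on score change alone:
- Day 1 = Day 71 = 3/3, later 3/3: change 0/0. No event; it stays in the denominator as if response were kept.
- Day 1 = Day 71 = 3/3, later 4/4: change 1/1, and worse than Day 1. It meets 1-level composite reduction and complete loss. It can never meet 2-level reduction.
- A score of 4 on either scale at Day 71: that scale cannot worsen, so no composite event is possible.
- Day 1 = 3/3, Day 71 = 2/3 (improved on one scale only), later 3/4: change 1/1 and not better than Day 1. It meets 1-level composite reduction and complete loss.

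**3. Effect on a tabulated rate.** All inputs are assumed, because the SAP gives none of them:
- u = share of subjects in a category with only one responding buttock, 10% to 60%
- p = event rate in responding buttocks, 30%
- q = event rate in non-responding buttocks, 0% or 10%, plus q = p
- f = u/2 = share of non-responding buttocks in a left or right table, with one-sided responders split evenly between sides

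Tabulated rate = (1 − f)p + fq. Restricted to responding buttocks, the rate is p = 30%.

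| u | f | q = 0 | q = 10% | q = p |
|---|---|---|---|---|
| 10% | 5% | 28.5% | 29.0% | 30% |
| 20% | 10% | 27.0% | 28.0% | 30% |
| 40% | 20% | 24.0% | 26.0% | 30% |
| 60% | 30% | 21.0% | 24.0% | 30% |

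In counts, for u = 40%: of 100 subjects in one category, 60 respond on both sides, 20 on the left only and 20 on the right only. The left table has 80 responding buttocks and 80 × 0.30 = 24 events. With q = 0 it reads 24/100 = 24% instead of 24/80 = 30%. With q = 10% it reads (24 + 2)/100 = 26%.

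For q = 0 the relative understatement is u/2, that is 5% to 30% over the range of u. If q exceeded p, the error would reverse. For complete loss this cannot be excluded, since an unchanged buttock needs only one level of worsening and a 2-level responder at least two.

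**The case against.** The strongest reply is that Table 16 already settles the matter. It defines the population that 7.6.2 uses and ties the evaluation to each treated buttock; nothing says 7.6.2 overrides it. On that reading Table 16 selects the buttocks and 7.6.2 only removes those already retreated. Table 13 also speaks of worsening of an improvement, and its times start when a composite improvement is assessed, so a buttock going from 3 to 3 to 4 had nothing to worsen. The layouts are in SAP Module 2, which is not at hand and may contain the strata. The analyses are descriptive, and display by category is a legitimate choice.

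Much of this stands. A reader might infer that non-responding buttocks will certainly be counted and the secondary objective contaminated; the documents do not support that, given Table 16 and the wording of Table 13. Nor is every such buttock one with nothing to lose, since some improved on one scale.

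The gap remains, however. Sections 7.6.2 and 7.6.3 neither repeat the buttock condition nor refer to it. For definitions they point to 4.4.1, which holds only change scores, and not to 4.4.2, where Table 13 is. Table 17 derives time to reduction from the Day 71 date with no response condition. An explicit denominator is what a programmer will follow.

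**Conclusion.** The point holds as an unreconciled conflict between the responder strata of Table 16 and the denominators and grouping of 7.6, 7.6.2 and 7.6.3. Under the literal denominators, a buttock without a composite response at the reference Day 71 is included, and a 1-level buttock of a Category II subject is reported under Category II.

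The net effect is probably an understated loss rate, which flatters durability, because unchanged buttocks and those already at the top of a scale add to the denominator without adding events. Neither size nor direction can be derived from the SAP: both depend on the share of one-sided responders and on the event rate in non-responding buttocks. A reader might take a figure such as 24% against 30% as the expected error; it is an illustration under assumed inputs, and the bias is zero if the two event rates are equal. The point is worth settling because it concerns the only secondary objective and the choice can change the tabulated rates.

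**What to change.** - In 7.6.2 and 7.6.3, limit each left/right denominator and each time-to-event set to buttocks with a composite response at the relevant Day 71: double-blind for 7.6.2, retreatment for 7.6.3. Keep the existing retreatment-status conditions.
- Stratify by that buttock's own response level, as Table 16 says. Subject category can stay as an additional display.
- Name the buttock as the unit in these tables, in place of the open choice in 7.6.2.
- State in Table 13 and Table 17 that reduction and complete loss require a composite response at the reference Day 71, and correct the references in 7.6.2 and 7.6.3 to point to 4.4.2.

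The cost is SAP wording, revised shells and smaller denominators. All the data needed are already collected.

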2.2. Secondary Objective

The secondary objective of this study is to assess the time to reduction of response (TRR) to CCH in the treatment of EFP in adult women.

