3.6. Determination of Sample Size

The study will rollover subjects who completed the respective double-blind studies and are willing to participate in the current study until the double-blind studies are unblinded, after which only active subjects (approximately 420 subjects who received CCH in the double-blind study) will remain in observation in this study. The sample size of approximately 420 should be adequate to determine long-term safety and time to reduction of response to CCH.

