2-level Composite Reduction	Worsening of cellulite severity improvement by at least 2-level on both PR-PCSS and CR-PCSS ratings compared to the score at Day 71/EOS (or Day 1) in the double-blind study.	Worsening of cellulite severity improvement by at least 2-level on both PR-PCSS and CR-PCSS ratings compared to the score at Day 71/End of Treatment Session in the open-label treatment phase.
1-level Composite Reduction	Worsening of cellulite severity improvement by only 1-level on both PR-PCSS and CR-PCSS ratings compared to the score at Day 71/EOS (or Day 1) in the double-blind study.	Worsening of cellulite severity improvement by only 1-level on both PR-PCSS and CR-PCSS ratings compared to the score at Day 71/End of Treatment Session in the open-label treatment phase.
Time to Composite Reduction of Response by 2-level	Number of days from the time of assessing composite improvement in cellulite severity on PR-PCSS and CR-PCSS at Day 71/EOS (or Day 1) in the double-blind study to the study visit prior to retreatment at which at least 2 level of worsening of response in both PR-PCSS and CR-PCSS ratings is observed for the first time.	Number of days from the time of assessing composite improvement in cellulite severity on PR-PCSS and CR-PCSS at Day 71/End of Treatment Session in the open-label treatment phase to the study visit during observation phase after retreatment at which at least 2 level of worsening of response in both PR-PCSS and CR-PCSS ratings is observed for the first time.
Time to Composite Reduction of Response by 1-level	Number of days from the time of assessing composite improvement in cellulite severity on PR-PCSS and CR-PCSS at Day 71/EOS (or Day 1) in the double-blind study to the study visit prior to retreatment at which only 1-level of worsening of response in both PR-PCSS and CR-PCSS ratings is observed for the first time.	Number of days from the time of assessing composite improvement in cellulite severity on PR-PCSS and CR-PCSS at Day 71/End of Treatment Session in the open-label treatment phase to the study visit during observation phase after retreatment at which only 1-level of worsening of response in both PR-PCSS and CR-PCSS ratings is observed for the first time.

Table 13: Reduction of Response (Continued)

Variables	Prior to Retreatment (including Through Day 180 Observational Period)	After Retreatment

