6. STATISTICAL METHODS

6.1. General Methodology

All summary tables and data listings will be prepared using version 9.4 or later of statistical analysis software (SAS®) software.

Continuous data will be summarized using descriptive statistics (number of subjects [n], mean, standard deviation [SD]/ or standard error [SE], median, minimum [min], and maximum [max]) and discrete data will be summarized using frequency counts and percentages, the denominator will be based on the number of subjects in the appropriate population. For the purpose of display, the summary results will be rounded as follows:

- Min and max: same number of decimal places as the raw data.
- Mean and median: one more decimal place than the raw data.
- SD/SE: two more decimal places than the raw data.
- Percentages will be displayed with one decimal precision. A zero count will not have the associated percentage presented on the table (ie, no 0%).
- The standard form of a percentage change variable is 0 decimal places.

For categorical variables with missing values, a category documenting the frequency of missing values will be displayed in the summary tables.

Summary tables, subject listings, graphs and any supportive SAS output will include a “footer” of explanatory notes that will indicate, when applicable:

- Date of data extraction
- Date and time of output generation
- SAS program name, including the path, that generates the output

When calculating percentages, the denominator will be based on the number of subjects with non-missing values. If the denominator is expected to change over time, then the denominator used to calculate the percentage should be based on the number of subjects with non-missing values at each visit. Any subject removed from an analysis will be noted at the bottom of the table along with the reason the subject was removed.

Null summary tables will be presented with a note stating that “No Subjects Met Criteria.” Subject listings of all data from the CRFs as well as any derived variables will be presented.

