Baseline for Reduction of response and Improvement in Cellulite Severity (CR-PCSS and PR-PCSS)	
Improvement in Cellulite Severity: The assessment performed at Day 1 during the retreatment phase will be used as baseline to evaluate improvement in cellulite severity at Day 71 in this study.
 
Reduction of Response Prior to Retreatment: The assessment performed at Day 71/EOS visit in the double-blind phase will be used as baseline to evaluate reduction of response for any visits prior to/on first dose date of retreatment in this study.
 
Reduction of Response After Retreatment: The assessment performed at Day 71/End of treatment Session in the retreatment phase will be used as baseline to evaluate reduction of response during the observation phase after retreatment.

Baseline for CR-PCSS, PR-PCSS and PR-CIS Score	
At 180 Day Evaluation: The Screening assessment done within 14 days of Day 71/EOS of double-blind period will be used as baseline for 180 Day Evaluation period.
 
Before Retreatment: The Screening assessment done within 14 days of Day 71/EOS of double-blind period will be used as baseline for open-label period for subjects in TRR population who are not retreated, and until the point prior to retreatment for the subjects who are retreated.
 
After Retreatment: The assessments at Screening B/unscheduled assessment or Day 1 of the retreatment phase prior to/on the first dose date of retreatment in this study will be used as baseline.

Baseline for S-GAIS and Subject Satisfaction with Cellulite Treatment	The pretreatment Day 1 digital images from the double-blind study (EN3835-302/303) will be used as baseline.
Change from Baseline	Change from baseline will be derived as, post-baseline visit/time point value – the baseline value.
Time to reduction of response prior to retreatment (duration in days)	Date of visit where reduction is detected first – Date of Day 71/EOS of double-blinded studies 302/303
Time to reduction of response after retreatment (duration in days)	Date of visit where reduction is detected first – Date of Day 71/End of Treatment Session of open-label retreatment phase
Time to Complete Loss of Response prior to retreatment (duration in days)	Date of visit where complete loss of response reduction is detected first – Date of Day 71 of double-blinded studies 302/303 OR Date of Day 71/End of Treatment Session of open-label retreatment phase

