6.3. Handling of Missing Data

Subjects who discontinue the study prior to or after the initiation of the study drug will not be replaced and available data of these subjects until the point of discontinuation will be summarized. The missing baseline assessment will not be imputed.

For categorical variables with missing values, a category documenting the frequency of missing values will be displayed in the summary tables.

Subjects who discontinue early will be requested to complete all EOS procedures and assessments at an early termination visit.

There will be no imputation of missing values for safety data, however missing relationship between AE and study drug will be considered as related to study drug following worst case principle. Missing severity of an AE will be summarized as a severe AE.

Immunogenicity samples with a positive titer value will undergo a log transformation for analyses. Samples with titer level less than 1 will be assigned or imputed as a log transformed titer of zero (0) for analyses.

PR-CIS total score when scores are missing

If scores on at least two of the 6 items are missing, then PR-CIS total score will be calibrated to 6 and computed as:

- Total PR-CIS Score = (Sum of the Scores ÷ Number of question answered) x 6

If scores on three or more of the six items are missing, then the PR-CIS total score will be set to missing.

PR-CIS abbreviated total score when scores are missing

If scores on at least of the 5 items are missing, the PR-CIS abbreviated total score will be computed as:

- Abbreviated total PR-CIS Score = (Sum of the Scores ÷ Number of question answered) x 5

If scores on three or more of the five items are missing, then the PR-CIS abbreviated total score will be set to missing.

Composite response when PR-PCSS and/or CR-PCSS component missing

If the classification is missing for 1 or both components (ie, the PR-PCSS component or the CR-PCSS component), then the composite responder classification is missing for that visit.

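### Time to reduction of response, the only secondary objective, is summarized only among subjects with a detected loss, with no censoring rule or time-to-event estimator, so slow loss is reported as too short

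*SAP*

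**What the plan says.** Section 2.2: "The secondary objective of this study is to assess the time to reduction of response (TRR) to CCH". No other secondary objective is listed. Section 3.6: "The sample size of approximately 420 should be adequate to determine long-term safety and time to reduction of response to CCH".

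Section 4.4.2, Table 13, counts days from Day 71 to a visit where loss is seen. For the 1-level composite the end point is the visit "at which only 1-level of worsening of response in both PR-PCSS and CR-PCSS ratings is observed for the first time". For complete loss the count runs "to the study visit prior to retreatment at which the complete loss of response in both PR-PCSS and CR-PCSS is observed". Table 17 in section 6.2 gives the same derivation as a date difference: "Date of visit where reduction is detected first – Date of Day 71/EOS of double-blinded studies 302/303". A subject with no such visit has no value.

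Sections 7.6.2 and 7.6.3 then ask for a descriptive summary. In 7.6.2 the times ("refer to section 4.4.1 for derivation) will be summarized descriptively using TRR Population Before Retreatment and OLNLR Population"); the cross-reference should be to 4.4.2, which contains no censoring rule either. Section 6.1 fixes what a descriptive summary is: "Continuous data will be summarized using descriptive statistics (number of subjects [n], mean, standard deviation [SD]/ or standard error [SE], median", with minimum and maximum. On early leavers, section 6.3 says only that "available data of these subjects until the point of discontinuation will be summarized". Table 18 ends pre-retreatment follow-up at retreatment but assigns no time to a subject who is event-free then.

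The other readout in 7.6.2 is the proportion with reduction at each visit, among subjects not yet retreated.

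**The concern.** These are right-censored, visit-detected times treated as complete continuous data. Three groups drop out of the summary: subjects event-free at Day 1080, subjects who leave event-free, and Category I subjects retreated without loss. The last group exists because Table 2, footnote n, asks Category I only for ratings of at least 2 on both scales and does not require a reduction.

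The mean and median then describe how quickly response was lost among those who lost it within three years. With slow loss they are governed by the visit days and the 1080-day limit. They also fall as more Category I subjects are retreated without loss, although durability is unchanged.

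The visit-wise proportions in 7.6.2 do not fill the gap after Day 180. A Category II subject with confirmed, eligible loss who accepts the optional retreatment leaves later denominators. The Open Label Not Retreated population does not repair this, because it is selected on later retreatment.

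At stake is whether the trial can answer its secondary objective: by the planned mean and median, a long-lasting response would look much like one that fades several times faster.

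**Working it through.** **The plan's own figure.** The 420 in section 3.6 is the number of active-treated subjects expected to roll over, half of the 840 in section 3.1 (420/840 = 0.5). No event rate or precision is given, so there is nothing to reproduce.

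**Inputs.** From the SAP: visits at Days 180, 360, 540, 720 and 1080 after double-blind Day 71. Assumed, because the SAP gives no rates: permanent loss with an exponential time; no dropout unless stated.

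**Formulas.** S(t) = exp(−ln 2 × t / true median). Probability of first detection at visit k: p_k = S(v_{k−1}) − S(v_k). Event-only mean = Σ p_k v_k / Σ p_k. Event-only median = first visit where the running sum of p_k / Σ p_k reaches 0.5. Share with no time = S(1080). True mean = true median / ln 2.

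**Worked case, true median 1080 days.** p = 0.1091, 0.0972, 0.0866, 0.0771, 0.1300; sum 0.500.
Mean = (0.1091×180 + 0.0972×360 + 0.0866×540 + 0.0771×720 + 0.1300×1080) / 0.500 = 297.3 / 0.500 = 595 days, against a true mean of 1080 / 0.6931 = 1558.
The running share is 0.41 at Day 360 and 0.59 at Day 540, so the median is Day 540.

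| True median (days) | True mean | Planned mean | Planned median | Share with no time |
|---|---|---|---|---|
| 720 | 1039 | 563 | 540 | 35% |
| 1080 | 1558 | 595 | 540 | 50% |
| 1800 | 2597 | 621 | 540 | 66% |
| 3600 | 5194 | 640 | 540 | 81% |

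A fivefold change in durability moves the mean by 640 − 563 = 77 days and the median by nothing. True medians off the visit grid (750, 900, 1500) give means of 567, 582 and 613, again with median 540.

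**Dropout.** With an assumed 12% a year (p_k multiplied by exp(−μ v_k), μ = −ln 0.88 / 365.25), the four means become 526, 556, 581 and 600.

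**Category I, true median 1080.** Suppose a fraction c of those event-free at Day 180 is retreated without loss before Month 12 (p_k multiplied by 1 − c from the second visit). For c = 30%, 60% and 90%, the mean falls from 595 to 559, 492 and 320 days, and the median is 540, 360 and 180.

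**After retreatment.** Retreated subjects rejoin a schedule counted from double-blind Day 71, so follow-up is shorter. For the same four true medians:
- Retreatment Day 71 assumed at study Day 280 (visits 80, 260, 440, 800 days later): means 470, 488, 503 and 514; 46% to 86% with no time.
- Assumed at Day 460 (visits 80, 260, 620 days later): means 413, 424, 433 and 439; 55% to 89% with no time.

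**Category II proportions before retreatment, true median 1080 (3-year loss 50%).** Let C be cumulative loss and r the share of losses confirmed, eligible and accepted for retreatment. Planned proportion = (p_k + (1 − r) C_{k−1}) / (1 − r C_{k−1}).

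| r | Month 24 (true 37%) | Month 36 (true 50%) |
|---|---|---|
| 25% | 32% | 45% |
| 50% | 26% | 39% |
| 80% | 18% | 29% |

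**What the remedy recovers.** For a true median of 1080, Kaplan-Meier on the visit grid gives 1080. For 1800 and 3600 it reports the median as not reached, with 66% and 81% still free of loss at Day 1080. For 750 and 900, grid Kaplan-Meier gives 1080 and an interval-censored estimate places the median only between Days 720 and 1080; both give Month 36 loss correctly (63% and 57%).

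**The case against.** **Fast loss.** The documents do not establish that loss is slow. On the same method, true medians of 180, 270, 360 and 540 days give planned medians of 180, 360, 360 and 540, the same as Kaplan-Meier on the visit grid. The planned means are 349, 426, 475 and 532 against true means of 260, 390, 519 and 779. So without removal the planned median does no harm up to about 18 months, and under fast loss the mean is too long. This stands. The bias claimed here is for slow loss, and the plan must work without knowing which case applies.

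**Visibility and other readouts.** The n beside each mean shows how many subjects lack a time, the Day 180 proportion is sound, and ratings are listed. These disclose part of the problem but do not supply an estimate. The denominator argument applies only to 7.6.2. In 7.6.3 the denominator is subjects already retreated, and only one course is allowed, so no one leaves by further retreatment. The narrower fault there is that each visit mixes different times since retreatment.

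**Status.** The study is open-label, its primary objectives are safety and immunogenicity, and no test is planned. But Kaplan-Meier and interval-censored estimates are themselves descriptive; the fault is bias in the estimate. The table shells (SAP Module 2) are not at hand, but the SAP text would still prescribe the descriptive summary.

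**Open details.** A loss may fail its confirmation visit, and Category I retreatment depends on current ratings, so censoring there may be informative. Sections 3.1.2 and 3.1.3 also describe later visits of retreated subjects as safety visits, while Table 3 schedules severity ratings and 7.6.3 analyses them. These points stand and belong in the fix.

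**Conclusion.** The concern holds. As written, the analysis of the sole secondary objective discards every subject without a detected loss. This is a wrong stated method, not missing detail. That it yields no time for event-free subjects follows from the SAP text alone; the size depends on assumed rates.

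With exponential permanent loss and no dropout, true medians from about 2 to 10 years produce one and the same planned median and nearly the same mean. Dropout and Category I retreatment without loss shorten the mean further. The direction is downward for slow loss, not in every setting. The retreatment and dropout rates used are illustrations without support in the documents. The plan should be changed before the analysis is run.

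**What to change.** - **Estimator.** In 7.6.2 and 7.6.3, replace the descriptive time summary with an interval-censored (Turnbull) estimate on actual visit dates. Kaplan-Meier on the visit grid is acceptable if labelled time to detection, since its median can fall only on a visit day.
- **Output.** By category and buttock, give the median (or not reached) and the cumulative probability of loss with 95% confidence intervals: at Months 6, 12, 18, 24 and 36 before retreatment, and by time since retreatment Day 71 after it.
- **Censoring.** Censor event-free subjects at the last PR-PCSS/CR-PCSS assessment before retreatment, withdrawal or end of study. Keep a subject who loses response and is then retreated as an event.
- **Event.** For this estimator, define the 1-level event as at least 1 level on both scales, so that a direct 2-level fall is not censored as continued response. State that first detection is the event, as in Table 17, and how an unconfirmed loss is treated.
- **Sensitivity.** For 2-level and complete loss, examine informative censoring by retreatment, for example by counting retreatment after confirmed loss as an event, as an upper bound. A similar check is advisable for Category I subjects retreated without loss.
- **Consistency.** Correct the cross-reference to 4.4.2, and reconcile sections 3.1.2 and 3.1.3 with Table 3 on severity ratings after retreatment.

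The cost is SAP wording and one standard procedure, using the severity ratings that Table 3 schedules. The price is that a median may be reported as not reached, or only as lying between two visits.
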